Will sample material be sold or transferred to any third parties? Will the information be de-identified?

no

If sample will be banked for future use:

Where will the sample be banked and for how long?

sample will not be banked

Does the banking institution have an approved policy for the distribution of samples?

If the entire sample will NOT be used during the course of this research study:

Will the remaining tissue be discarded? If not what will be done with the remaining sample after study completion and how long will the sample be kept?

Remaining sample will be discarded appropriately

Will samples be made available to the research subject (or his/her medical doctor) for other testing?

No

If a subject withdraws from the study:

Will subject have the option to get the remaining portion of their sample back?

No

Will samples be destroyed? If not, will they be kept anonymously? What will happen to the sample if the subject revokes authorization?

Remaining sample will be discarded appropriately

Will data obtained from their sample be deleted? What will happen to the sample if the subject revokes authorization?

Data from the sample will not be deleted as long as subject remains on study.

Will study data or test results be recorded in the subject's medical records?

Yes

Will results of specific tests and/or results of the overall study be revealed to the research subject and or his/her doctor?

Yes, subject will be notified of results and instructed to contact primary care physician if needed.

Please identify all third parties, including the subject's physician, to receive the test results.

Section O: Drug Studies

Does the research involve the use of ANY drug* or biologic? (*A drug is defined as any substance that is used to elicit a pharmacologic or physiologic response whether it is for treatment or diagnostic purposes)

No

Does the research involve the use of ANY gene transfer agent for human gene transfer research?

No

O1. Current Drugs

Is this study placebo-controlled?

No

Will the research involve a radioactive drug?

No

Section P: Device Studies

Does this research study involve the use of ANY device?

Yes

[Device 1: vaginal stent](#)

Section Q: Consent Form(s)

Vaginal Stent Study in Healthy Participants

Vaginal stent to improve post-surgical outcomes and gynecologic cancer treatment

Section R: Advertisements

None

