Specific Aim I: Finalize design for a clinical-ready version of our vaginal stent system and perform preliminary verification and validation testing.

1a: Optimize the stent design. Biotex engineers will integrate our current prototype designs into two different inflatable configurations which cover desired diameters and length ranges. Efficacy of our vaginal stent is shown by its retention in the vaginal canal for 2 weeks. We will work closely with clinical collaborators to refine our stent designs as well as insertion and retrieval tools with the goal to finalize stent materials, size ranges, and factors which will improve patient compliance with stent use.

1b: Completion of product testing required for FDA submission and commercialization. Vital steps towards enabling product distribution include performing required validation activities (biocompatibility, sterilization, packaging,

performance testing) for FDA 510(k) submission. After finalization of stent designs, product development engineers will develop protocols under design controls, manage production of final units, and execute required testing.

Specific Aim II: Examine the acceptance and success of our novel vaginal stent in healthy (non-clinical) subjects. Accruing clinical samples large enough for both development and testing can be prohibitive due to the low numbers of adolescent patients at any one institution requiring neovaginal surgery. In addition, clinical samples can be heterogeneous on key variables which may relate to the success of our stent, such as age, maturity, or comorbid conditions. Therefore, we will conduct aim 2 in a non-clinical population.

2: Quantify key factors to better understand stent efficacy. In 20 non-clinical volunteers, we will associate factors such as design, pull-out forces, comfort, and inflation/ deflation / retrieval ergonomics with stent retention.

Specific Aim III: Evaluate the success of our vaginal stent in a broad cohort of clinical subjects. After establishing the regulatory (aim 1), practical (aims 1 and 2) and patient factors (aim 2), we will use this information to inform the protocol of our pseudo-clinical trial in aim 3.

3a: Demonstrate vaginal stent retention in the vaginal canal for two weeks in a clinical population. In 10 post-surgical patients and 10 post-radiation adult women, the efficacy of our novel vaginal stent will be demonstrated both through lack of egress and through patient compliance to using the device.

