Select one category that most adequately describes your research:

K) Device, Phase II, Single Center

Discuss the research design including but not limited to such issues as: probability of group assignment, potential for subject to be randomized to placebo group, use of control subjects, etc.

This is a non-randomized clinical trial of healthy and patient cohorts, females ages 13-64 years will be recruited into different groups. 20 healthy participants (ages between 13-64 years) will be recruited initially to try wearing 2 stents separately for 24 hours each, provide feedback, then wear the preferred stent for 2 weeks. Subsequently, 20 patient participants, 10 post-surgical adolescent patients and 10 post-radiation adult patients, will be recruited to wear the stent for 2 or 4 weeks, respectively. Neither healthy nor patient participant will be randomized. (Procedure details in section F2.) A control cohort will not be recruited; rather, within-group outcomes will be measured. The adolescent versus adult female patient outcomes will also be compared.

Physician participants will be asked to complete a post-stent questionnaire which will evaluate the level of difficulty with stent insertion and removal.

Inclusion Criteria:

Healthy volunteers: (a) female between 13-64 years of age, (b) not currently pregnant, (c) if under age 18, parents must be able to give informed consent and volunteer must give informed assent, (d) ability to understand the requirements of the study and abide by the restrictions, (e) ability to travel to Houston for study evaluations, (f) ability to understand English or Spanish to a grade 5 level, (g) no history of prior vaginal surgery or radiation.

Patient volunteers: (a) adolescent female patients, ages 13-18 undergoing vaginal reconstructive surgery at high risk for vaginal fibrosis including those with transverse vaginal septa, vaginal atresia, or post-radiation, (b) adult female patients undergoing vaginal brachytherapy for cancer at high risk of vaginal fibrosis, (c) not currently pregnant, (d) ability to give informed consent (If patient is under age 18, must be able to give informed assent with parent consent), (e) ability to understand the requirements of the study and abide by the restrictions, (f) ability to travel to Houston for study evaluations, (g) ability to understand English or Spanish to a grade 5 level.

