b) Adult Females, Post-Radiation: Post-radiation vaginal fibrosis occurs more slowly than post-surgical fibrosis and these women do not have post-surgical wounds, so we expect the adult post-radiation patient population to be able to wear the vaginal stent continuously for two weeks and then for an additional 2 weeks. Following consent adult patients undergoing vaginal brachytherapy treatments, will complete Pre-Stent Questionnaire and the vaginal stent will be placed by [name] or another co-investigator physician at the conclusion of their final brachytherapy treatment. Prior to stent placement, the vaginal canal and mucosa will be assessed by speculum exam, vaginal culture, urine pregnancy test, and urinalysis will be obtained and the physician will complete the VAF. Instructions will be given to the patients prior to discharge. If the participant is at a high risk for tissue erosion, per physician discretion, she will be prescribed a topical vaginal estrogen (e.g. Premarin cream or Repagyn hyaluronic acid gel). It is SOC to prescribe vaginal estrogen to current patients with vaginal stents or pessaries who are at higher risk for tissue erosion (e.g. post-menopausal patients); thus, use of the cream or gel in the current study is not experimental. Participants will be sent a secure link to complete a daily questionnaire on retention and comfort.

Evaluation at 2 and 4 weeks: Patients will be examined in clinic by a physician co-investigator at 2 weeks post-stent placement. At the time of assessment, patients will complete evaluation surveys on the vaginal stent as well vaginal symptoms such as pain or bleeding. The vaginal stent will be removed and the vaginal cavity will be assessed by a physician for any adhesions, granulation tissue, stricture, fibrosis, necrosis by speculum exam and vaginal culture. Vaginal length will be measured. Physicians will also rate ease of stent removal and complete VAF for each patient. Any patient-reported symptoms will be documented. At 2 weeks, if no AEs are reported, vaginal stent will be replaced by a physician for an additional two weeks of use. If AEs are reported, clinical decisions regarding continued use of stent will be made. Participants will be sent a secure link to complete a daily survey. If no AE seen in first three patients, clinician may determine two week follow up is not necessary and patients can wear stent for four weeks continuously.

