Analyses of 20 clinical patient participants: Initial analyses will compare the two patient groups on baseline characteristics (vaginal cavity assessments by physicians and patient and physician questionnaires) using two sample t-tests, specifying patient group as the predictor. T-tests were selected for the robust to non-normal distributions with small sample sizes, and their suitability to small sample sizes as low as four per group (ref: york.ac.uk/depts/math/histstat/student.pdf). Our main analyses will examine whether the stent was successful in our population (ie. examining whether the proportion of retained stents was significantly different from zero). A one-sample t-test will be run, with success (returned at 2 weeks coded as 1, not retained coded as 0) as the independent variable. Significance will be set at $P < .05$.

All analyses will be conducted in the latest version of R (version 5.1.2).

Section H: Potential Risks/Discomforts

H1. Potential Risks/Discomforts

Describe and assess any potential risks/discomforts; (physical, psychological, social, legal, or other) and assess the likelihood and seriousness of such risks:

The participant may experience mild discomfort while using the stent. A thorough vaginal assessment will be performed by a clinician immediately after insertion to assess for any discomfort outside of normal range.

The likelihood of adverse events is small but could include bleeding, displacement of the stent such as egress, urinary retention, mucosal irritation, tearing, erosion, abscess, granulation tissue, or infection. The principal investigator will likely stop the trial for persistent displacement (>5), tearing or erosion of tissue, or abscess. The principal investigator will likely pause the trial and assess for further detail in instances of urinary retention, mucosal irritation, granulation tissue, or infection.

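### The main retention test in G2 pools post-surgical and post-radiation patients with no group term, so it can declare success when the stent has failed completely in one of the two indications.

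*Combined protocol and SAP*

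**What the plan says.** The patient part of Section G2 is headed "Analyses of 20 clinical patient participants". Its main question is put for one population: "Our main analyses will examine whether the stent was successful in our population". G2 then glosses success as "examining whether the proportion of retained stents was significantly different from zero". The method is one test: "A one-sample t-test will be run, with success (returned at 2 weeks coded as 1, not retained coded as 0) as the independent variable". I read the word for the event coded 1 as meaning retained. The level is 5%, with sidedness not stated. No group term, cohort-specific proportion or per-cohort success rule appears. The only comparison of the two patient groups that G2 specifies is on baseline characteristics.

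Other sections treat the cohorts as distinct:

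- **Section D, Aim 3a** sets the composition: "In 10 post-surgical patients and 10 post-radiation adult women".
- **Section D, Aim 3b** rests on the number of stents in place two weeks after neovaginal surgery, set against handmade stents. That is a surgical-only count.
- **F1** says "A control cohort will not be recruited; rather, within-group outcomes will be measured", and adds at once that adolescent and adult patients will be compared on outcome. It names no endpoint or test.
- **F2, Phase 3(b)** separates the indications: "Post-radiation vaginal fibrosis occurs more slowly than post-surgical fibrosis and these women do not have post-surgical wounds".

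**The concern.** A single proportion over 20 patients, half from each indication by design, averages two settings that the protocol itself distinguishes. Planned wear also differs (two weeks or four), although retention is tested at two weeks in both. A significant pooled result says only that some stents stayed in somewhere. Because G2 equates that result with success, the statement would cover both indications even if every retained stent came from one of them. G1 says the participants will guide further refinement of the device, and that requires knowing in which indication it fails.

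**Working it through.** **Inputs.** There are 10 post-surgical and 10 post-radiation patients (Aim 3a, F1). Retention is coded 0/1 at two weeks, the null proportion is 0 and alpha is 0.05 (G2). I take the test as two-sided. The documents give no expected retention rate, so the rates in step 3 are assumptions.

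**1. The plan's own figure.** G1 gives a headcount of 40 and no power or precision calculation. 20 healthy + 10 surgical + 10 radiation = 40, which agrees. F2, Phase 3 states 20 patients but lists 20 adolescents and 10 adults. That gives 20 + 20 + 10 = 50, which does not agree.

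**2. The planned test.** For k retained of n, with p = k/n, t = p / sqrt(p(1 − p)/(n − 1)) on n − 1 degrees of freedom.

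- 3/20: t = 0.15 / sqrt(0.15 × 0.85/19) = 1.83, p = 0.083.
- 4/20: t = 0.20 / sqrt(0.20 × 0.80/19) = 2.18, p = 0.042.
- 10/20: t = 0.50 / sqrt(0.50 × 0.50/19) = 4.36, p = 0.0003.

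The pooled test therefore passes from 4/20 (from 3/20 if one-sided, p = 0.041). Both 0/10 with 4/10 and 0/10 with 10/10 pass. The statistic is undefined at 0/20 and 20/20, where the variance is zero. With 30 patients, as F2's list implies, 4/30 gives t = 2.11, p = 0.043, so the conclusion is the same.

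**3. How often one cohort can carry the result.** If one cohort's true retention is 0%, the pooled count is Binomial(10, q), where q is the other cohort's rate. The test passes when that count is at least 4.

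| q (assumed) | P(pooled test significant) |
|---|---|
| 30% | 35% |
| 40% | 62% |
| 50% | 83% |
| 60% | 95% |
| 70% | 98.9% |

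**4. What cohort-specific reporting shows.** Exact (Clopper-Pearson) 95% intervals for n = 10:

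- 0/10: 0% to 30.8% (upper limit 1 − 0.025^(1/10)).
- 4/10: 12.2% to 73.8%.
- 10/10: 69.2% to 100%.

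**5. What splitting does not cure.** Within one cohort, 4/10 against zero gives t = 0.40 / sqrt(0.40 × 0.60/9) = 2.45, p = 0.037. The null of zero would still credit 40% retention.

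**6. Whether a between-group comparison would catch it.** Fisher's exact test gives p = 0.00001 for 0/10 versus 10/10, but p = 0.087 for 0/10 versus 4/10. With assumed true rates of 40% and 90%, its power is about 47%.

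**The case against.** The best defence is that the protocol does not ignore the cohorts. F1 promises within-group outcomes and an adolescent-versus-adult comparison, and Aim 3b cannot be carried out without a surgical-only count. With 10 patients per cohort, the split counts would very probably be reported. This stands against a stronger inference that a reader might draw, namely that failure in one indication would stay hidden in the study report. The documents do not support that. What remains is that F1 names no endpoint, test or success rule, that G2 gives no method for Aim 3b, and that the analysis G2 calls main is unaffected by either. Step 6 shows that a non-significant comparison would not be reassuring.

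A second defence is that the null of zero does most of the damage. That is correct. It follows that not every discordant pair shows harm from pooling: with 4/10 and 9/10, both cohorts would pass the planned test on their own. Pooling alters the verdict where a cohort would not pass alone, as at 0/10.

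Two further inferences should be resisted. G2 compares the groups at baseline but never offers those t-tests as grounds for pooling. F2 describes slower fibrosis and absence of wounds after radiation, but does not say that two-week retention will differ.

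Finally, G1 calls this a feasibility study, so no power per cohort is expected. That argues against asking for more patients, but not against separate estimates.

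**Conclusion.** The point holds for the main analysis in G2. As written, that analysis can return success with no stents retained in one indication and 4 of 10 in the other, and under the assumed rates it would do so often (62% to 95% for 40% to 60% retention in the other cohort, with none in the first). This rests on reading one test under a heading of 20 patients as pooled, which is the plain sense although G2 does not use the word, and on a two-sided 5% level. Pooling and the null of zero are separate faults. The null is the larger one, and both need correcting. The disagreement over the number of adolescents does not change the conclusion.

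**What to change.** In G2:

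1. Make the main result the two-week retention proportion in each cohort, with an exact (Clopper-Pearson) 95% interval, in place of the pooled t-test.
2. State success for a cohort only if its own interval supports it against a non-zero retention benchmark, fixed and justified before the data are seen. With 10 patients the lower limit cannot exceed 69.2% (at 10/10). If the justified benchmark is at or above that, report the estimates without a success statement.
3. Name two-week retention as the endpoint of F1's adolescent-versus-adult comparison, and give the method.
4. Report the pooled proportion, if at all, as descriptive.

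Also reconcile the 20 adolescents in F2, Phase 3 with the 10 in F1 and Aim 3a and with the total of 40 in G1.

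The cost is wording and the work of justifying a benchmark. No patients, visits or data are added. The price is precision: at 50% retention the exact interval is 27% to 73% for 10/20, but 19% to 81% for 5/10.
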